2.3. Protocol Deviations/Violations

Protocol deviations and violations will be summarized outside of this statistical analysis plan.

2.4. Study Day and Treatment Period

Study day is defined as

- Event Date – First Dose Date + 1 if the event date is on or after the first dose date
- Event Date – First Dose Date if the event date is before the first dose date

Study Day 1 is defined as the first dose date.

Treatment period is defined as the number of days from the first dose date to the last dose date + 7. The duration of treatment is defined as last dose date + 7 – first dose date + 1.

2.5. Study Endpoint Baseline

In general, the baseline of a study endpoint is the last observation prior to the first study drug administration except for platelet count.

The baseline of a laboratory parameter will be based on the central laboratory values except for platelet count.

Platelet counts from the central laboratory are to be used in the calculation of baseline. If a central laboratory value is not available and its local laboratory value is available on the same collection date, the local laboratory value will be used. In addition, if there are at least 2 platelet count collections on the same date, the first one will be used.

Baseline platelet count is defined as the average of values obtained on different days in the week (including Day 1) prior to the first dose of OMS721. If more than 3 such values are available, then the 3 values that are most proximate to the first dose of OMS721 should be used. [Table 2](#) is an example of a baseline platelet count calculation.

Table 2: Example of Baseline Platelet Count Calculation

Study Day	Central Lab	Local Lab	Value to be used to Determine Baseline
-5	Yes	Yes	Not used
-4	Yes	Yes	Central lab
-3	No	Yes	Local lab
-2 (1 st)	No	Yes	Not used
-2 (2 nd)	Yes	No	Central lab
-2 (3 rd)	Yes	Yes	Not used

In addition, if at least 1 central laboratory value is used in the baseline calculation, the reference range of the central laboratory will be used to determine the toxicity grade according to National Cancer Institute (NCI) Common Terminology Criteria for Adverse Events (CTCAE). If the baseline value is calculated from local laboratory values only, then the reference range of the local laboratory will be used.

2.6. Analysis Visits and Time-points

In general, analysis visit windows will be defined approximately equally over adjacent scheduled visits (Table 3).

Table 3: Analysis Visits for Data Collected at Scheduled Visits

Scheduled Visit	Target Day [Week]	Visit Window (Study Days)
Screening	-28 [-4]	≤ -1
Day 1	1 [1]	1
Week 1	1 [1]	1 to 4
Week 2 to 9	$(w-1)7 + 1$ [w]	$(w-1)7 - 2$ to $(w-1)7 + 4$, w = 2 to 9
Week 10	64 [10]	61 to 71
Week 12	78 [12]	72 to 81
Week 13	85 [13]	82 to 130
Week 26 to 104, every 13 weeks	$(w-1)7 + 1$ [w]	Ceiling of $(w-13+5.5)7 + 1$ to Integer of $(w+5.5)7 + 1$, w = 26 to 104, every 13 weeks

If there are multiple values collected during a scheduled visit window and only 1 of the values is necessary for an analysis, the value that is closest to the target day will be used. If there are 2 values that are equally spaced from the target day, the latest one will be used in the analysis, unless otherwise specified. Exceptions are given below:

- For multiple platelet counts and Hgb concentrations collected on the same day, the first measure of the day will be used to avoid confusion when transfusions may have been administered during the day.

- For transfusion data, if there are at least 2 transfusions of the same type given on the same day, the first transfusion will be used in the analysis.

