5 (N = 40 TTP or HSCT-TMA) As of Amendment 10, TTP enrollment is closed	2	OMS721 Dose 4.0 mg/kg IV weekly x 4 As of Amendment 10, the dose is changed to 370 mg IV weekly x 4
5 (N ≤ 40 TTP or HSCT-TMA) As of Amendment 10, TTP enrollment is closed	3	OMS721 Dose 4.0 mg/kg IV weekly x 4 As of Amendment 10, the dose is changed to 370 mg IV weekly x 4

Abbreviations: aHUS = atypical hemolytic uremic syndrome; HSCT-TMA = hematopoietic stem cell transplant-associated thrombotic microangiopathy; IV = intravenous; TTP = thrombotic thrombocytopenic purpura.

The **Stage 1** study schedule included 9 visits across 3 periods. Stage 1 is complete.

Period 1 – Screening (Visit 1, up to 4 weeks)

Period 2 – Treatment (Visit 2 to Visit 5, 4 weeks)

CONFIDENTIAL

No use, disclosure, or reproduction outside of Omeros without prior written authorization

Period 3 – Follow-up (Visit 6 to Visit 9, 8 weeks)

The length of time for individual patient participation was approximately 12 to 16 weeks.

The **Stage 2** study schedule for the **aHUS** cohort (Cohort 4) included 17 visits across 3 periods:

Period 1 – Screening (Visit 1, up to 4 weeks)

Period 2 – Treatment (Visit T-1 to Visit T-12, 12 weeks)

Period 3 (if patient did not continue to Stage 3) – Follow-up (Visit F-1 to Visit F-4, 6 weeks)

The length of time for individual aHUS patient participation in Stage 2 was approximately 18 to 22 weeks, depending on the time from screening to the first dose of OMS721 administration. Patients entering Stage 3 did not undergo the follow-up visits in Stage 2. The **Stage 3** study schedule for the **aHUS** cohort included 16 visits across 2 periods.

Period 2 (continued from Stage 2) – Treatment (Visit T-13 to Visit T-24, 12 weeks)

Period 3 – Follow-up (Visit F-1 to Visit F-4, 6 weeks)

The length of time for individual aHUS patient participation in Stage 3 was approximately 18 weeks, and the total length of time in Stage 2 and Stage 3 was approximately 30 to 34 weeks, depending on the time from screening to the first dose of OMS721 administration in Period 2.

As of Amendment 10 of this protocol, Cohort 4 was closed. As of Amendment 11 of this protocol, enrollment in the study has been completed.

The **Stage 2** study schedule for the **TTP/HSCT-TMA** cohort (Cohort 5) includes 9 visits across 3 periods:

Period 1 – Screening (Visit 1, up to 4 weeks)

Period 2 – Treatment (Visit T-1 to Visit T-4, 4 weeks)

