Patients with aHUS who completed Stage 2 treatment may have been eligible for an additional 12 weeks of treatment if the Investigator believed the patient was at risk for relapse of TMA, the patient tolerated OMS721 treatment, and the patient had no conditions that increase the risk of OMS721 treatment (e.g., serious active infection). The patient's treating Investigator and the Sponsor's medical monitor determined eligibility for Stage 3 based upon the patient's response to therapy and safety and tolerability prior to the last scheduled treatment visit in Stage 2 in order to determine the appropriate PK draws following that visit. Patients entering Stage 3 did not undergo the Follow-up visits in Stage 2.

Figure 3: Stage 3 Study Design Schematic (aHUS Cohort)

The **Stage 3** study schedule for the aHUS cohort (Cohort 4) includes 16 visits across 2 periods:

Period 2 (continued from Stage 2)-Treatment (Visit T-13 to Visit T-24, 12 weeks)

Period 3 - Follow-up (Visit F-1 to Visit F-4, 6 weeks)

[figure not shown]
The length of time for individual aHUS patient participation in Stage 3 was approximately 18 weeks and the total length of time in Stage 2 and Stage 3 was approximately 30 to 34 weeks. Follow-up visits occurred on Day 169, Day 176, Day 190, and Day 204.

The overall study was planned to take approximately 48 months to complete (from first patient visit to last patient visit).

TTP/HSCT-TMA Cohort

The Stage 2 and Stage 3 study designs are illustrated in [Figure 4](#) and [Figure 5](#) for the HSCT-TMA cohort. As of Amendment 10 of this protocol, enrollment of TTP patients was closed. As of Amendment 11 of this protocol, enrollment in the study has been completed.

Figure 4: Stage 2 Study Design Schematic (HSCT-TMA Cohort)

CONFIDENTIAL

No use, disclosure or reproduction outside of Omeros without prior written authorization

The **Stage 2** study schedule for the HSCT-TMA cohort (Cohort 5) includes 4 doses with up to 9 visits across 3 periods:

Period 1- Screening (Visit 1, up to 4 weeks)

[figure not shown]
Period 2-Treatment (Visit T-1 to Visit T-4, 4 weeks)

Period 3 (if patient does not continue to Stage 3)-Follow-up (Visit F-1 to Visit F-4, 10 weeks)

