3.4.2. Clinical Laboratory Tests

Statistical analysis of clinical laboratory tests, except for those as secondary endpoints (platelet count, LDH, creatinine, hemoglobin and haptoglobin) will be based on the results from central laboratories only. Results from central and local laboratories will be listed.

Summary statistics for the actual values and the change from baseline will be tabulated for laboratory results by dose, disease, and scheduled visit. Patients with laboratory values outside of the normal reference range at any post-baseline assessment will be summarized by dose and disease. Shift tables comparing the baseline NCI CTCAE grade to the worst post-baseline grade will be provided by dose and disease. These laboratory summary tables will exclude the laboratory tests that are the efficacy endpoints (Section 2.1).

Laboratory results may be presented graphically over the study scheduled visits, e.g., using box plots.

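### SAP Table 3 has no analysis visit between Day 85 and Day 176, so the by-visit chemistry and hematology tables for aHUS show no draw from Stage 3 dosing after its first dose

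*SAP*

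**What the plan says.** SAP Section 2.6 states the principle that "analysis visit windows will be defined approximately equally over adjacent scheduled visits". Table 3 then lists targets weekly up to Week 10 (Day 64, window 61 to 71), followed by Week 12 (Day 78, window 72 to 81) and Week 13 (Day 85, window 82 to 130). From Week 26 the windows come from a formula: "Ceiling of $(w-13+5.5)7 + 1$ to Integer of $(w+5.5)7 + 1$, w = 26 to 104, every 13 weeks". The selection rule has a condition, "If there are multiple values collected during a scheduled visit window and only 1 of the values is necessary for an analysis", and a consequence: "the value that is closest to the target day will be used".

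The protocol's aHUS calendar (Sections 7.1.2 and 19.2) has 12 weekly doses in Stage 2, T-1 on Day 1 to T-12 on Day 78. Stage 3 adds 12 more, T-13 on Day 85 to T-24 on Day 162. After Stage 3, "Follow-up visits occurred on Day 169, Day 176, Day 190, and Day 204".

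SAP Section 3.4.2 says "Summary statistics for the actual values and the change from baseline will be tabulated for laboratory results by dose, disease, and scheduled visit". It leaves platelets, LDH, creatinine, hemoglobin and haptoglobin out of those tables. Section 3.4.3 plans the same kind of by-visit table for vital signs.

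**The concern.** The 16 visits of aHUS Stage 3 (12 dosing, 4 follow-up) share two analysis rows, and neither target day falls among the dosing visits after the first. That conflicts with the SAP's own principle for building the windows, and no other part of the SAP gives windows for aHUS.

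Safety, including laboratory tests and vital signs, is a co-primary endpoint that expressly covers aHUS (SAP Section 2.1). Protocol Section 7.4 makes the assessment of safety during extended treatment a secondary objective of the Stage 3 extension. A by-visit table is where a mean trend in, say, ALT, AST, bilirubin or neutrophils would be seen. If it skips the period when doses 13 to 24 were given, a shift that appears on treatment and reverses within two weeks of the last dose leaves no trace in it.

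**Working it through.** **Inputs.** Windows, target days and selection rule: SAP Section 2.6 and Table 3. Visit days: protocol Sections 7.1.2 and 19.2. Sampling: protocol Sections 10.1.2.5 and 10.1.2.6 and the schedule in 19.2. At dosing visits all four laboratory panels are drawn before the dose. At Stage 2/3 follow-up only hematology, chemistry, LDH and haptoglobin are drawn; coagulation, urinalysis and vital signs are not scheduled there.

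**Reproducing Table 3.** Target day = (w−1)×7+1 gives 64, 78 and 85 for Weeks 10, 12 and 13, as stated. The stated Week 13 upper limit follows from the later formula: integer of (13+5.5)×7+1 = integer of 130.5 = 130. All windows are contiguous. The fault is in the list of target days, not in the window arithmetic.

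**Week 26.** Target (26−1)×7+1 = 176. Lower bound: ceiling of (26−13+5.5)×7+1 = ceiling of 130.5 = 131. Upper bound: integer of (26+5.5)×7+1 = integer of 221.5 = 221.

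**Dosing days.** Visit T-i falls on Day 1+7(i−1): T-10 = 64, T-11 = 71, T-12 = 78, T-13 = 85, T-14 = 92, T-23 = 155, T-24 = 162.

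**Selection for a patient completing both stages on the nominal days:**

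| Window | Days falling in it | Chemistry, hematology | Coagulation, urinalysis, vital signs |
|---|---|---|---|
| Week 10 (61–71) | 64, 71 | 64 (T-10) | 64 (T-10) |
| Week 12 (72–81) | 78 | 78 (T-12) | 78 (T-12) |
| Week 13 (82–130) | 85, 92, 99, 106, 113, 120, 127 | 85 (T-13) | 85 (T-13) |
| Week 26 (131–221) | 134, 141, 148, 155, 162, plus 169, 176, 190, 204 where sampled | 176 (F-2) | 162 (T-24) |

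T-1 to T-9 each have their own window.

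- Chemistry and hematology: T-11 and T-14 to T-24 are never selected, 1 + 11 = 12 of 24. F-2 is 176 − 162 = 14 days after the last dose.
- Coagulation, urinalysis and vital signs: T-11 and T-14 to T-23 are never selected, 1 + 10 = 11 of 24.

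**Sensitivity.** If the F-2 draw is missing, Week 26 takes Day 169, 7 days after the last dose. If there are no follow-up draws at all, it takes Day 162.

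**The case against.** The strongest reply is that little is lost. SAP Section 3.4.2 lists all central and local results, counts patients out of range at any time after baseline, and shifts baseline grade to worst grade. None of these is restricted to one value per window, and the group is small. Safety analysis is descriptive, the efficacy focus is HSCT-TMA, and the TMA markers are outside these tables. All of this stands and limits the weight of the point. It does not remove it: those outputs show extremes or single patients, not the course of the group over time. For vital signs, Section 3.4.3 names only the by-visit table and optional graphs.

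One could also say that tables by scheduled visit might use the visit label on the case report form rather than Table 3. The SAP does not say so. Table 3's first column carries that name, and Section 2.8.2.2.4 points to Section 2.6 for the scheduled visits.

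Four stronger readings are tempting, and the documents do not support them:

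- That every laboratory panel is blank during Stage 3. Coagulation and urinalysis keep T-24, drawn after 11 Stage 3 doses.
- That Table 3 simply follows the TTP/HSCT-TMA calendar. Day 85 is an aHUS visit (T-13, or F-1 for those who stopped) and is not on that cohort's schedule.
- That the Week 13 laboratory value mixes patients with different exposure. T-13 blood is drawn before dosing, so continuing and stopping patients alike have had 12 doses and are 85 − 78 = 7 days past the last one.
- That aHUS TMA-marker summaries share the gap. Protocol Section 13.2.8 plans them by disease and mentions no visit.

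**Conclusion.** The point holds for the by-visit safety tables in aHUS. Applied as written, SAP Section 2.6 produces chemistry and hematology tables with nothing from the 11 draws on Days 92 to 162, and it never selects 12 of 24 dosing-visit sets. For coagulation, urinalysis and vital signs the loss is 11 of 24, with one value, T-24, retained from late in Stage 3.

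This rests on nominal visit days, on a patient completing both stages, and on scheduled visit meaning the rows of Table 3. The number of patients affected is unknown. SAP Table 1 lists 14 + 4 = 18 aHUS patients in Cohort 4, which is the ceiling, and the number entering Stage 3 is not given.

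No data are lost and no efficacy result or decision rule changes. It is worth correcting because the tables would miss the period that the extension's own safety objective concerns, and because the correction is cheap.

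**What to change.** For the aHUS by-visit tables only:

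- Add weekly windows, target day ±3, for Weeks 11 to 24 (targets Day 71 to Day 162; windows 68–74 up to 159–165). End Week 10 at Day 67, which is what the Week 2 to 9 formula gives: (10−1)×7+4 = 67. The windows are then contiguous and each dosing visit has its own row.
- Place values dated after the day of a patient's last dose in follow-up rows by days since that dose, with targets 7, 14, 28 and 42. These match both aHUS calendars: Days 85, 92, 106 and 120 after Day 78, and Days 169, 176, 190 and 204 after Day 162. Set the bounds at the midpoints, (7+14)/2 = 10.5, (14+28)/2 = 21 and (28+42)/2 = 35, and say which row takes a value that falls on a midpoint.
- Let the follow-up rule take precedence over the calendar windows, so that a patient who stops early is placed once.

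Leave the HSCT-TMA windows unchanged.

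The cost is a SAP table edit and programming on data already collected. Some rows will have few patients. Day 85 draws will appear in two rows (Week 13 and first follow-up) although exposure at that draw is the same, so a footnote should warn against reading a difference between them as a treatment effect.

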2.7. Handling of Missing Data

The following general methods will be used for producing the data summaries and the manner in which missing data will be documented:

- Available clinical data at each visit will be presented and the sample size displayed will reflect the patients with available data. Patient listings data will be provided as recorded on the case report form indicating partial dates and missing data.
- Generally, if data are missing or incomplete, the missing values will be indicated and incomplete values will be presented in the data listings. Analyses will be based on the observed data without imputation unless otherwise specified.

The TMA diagnosis date must have at least the month and the year. If the day is missing, the day will be imputed as 1.

Non-responder imputation will be used to handle missing data for the binary efficacy endpoints. Time-weighted average analysis and repeated measures models will be used to analyze the continuous secondary efficacy endpoints over time.

For patients whose death dates are incomplete, if only the day of the death date is missing, the day will be imputed as the first day of the month. If either the month or the year of the death date is missing, the death date will not be imputed, and the overall survival will be censored at the last known date of alive in the database. For the patients who are alive, overall survival will be censored at the last known date of alive in the database.

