13.2.5.2. Analysis of Secondary Efficacy Endpoints

The 100-day survival status will be determined as a binary variable. A patient achieves a 100-day survival if the overall survival from the date of HSCT-TMA diagnosis of the patient is ≥ 100 days. If the 100-day survival status of a patient is unknown (i.e., censored before 100 days), this patient will be considered to have died prior to 100 days. The 100-day survival rate will be estimated with exact 95% CI by dose for the FAS population.

Overall survival will be calculated from the date of TMA diagnosis. Overall survival will be analyzed using Kaplan-Meier method by dose for the FAS population. Median overall survival and its 95% CI will be estimated by dose.

The duration of response will be estimated for the FAS population. Duration of response is defined as the number of days from the first response date to the first relapse date (first relapse date – first response date + 1). The first response date is the first date that platelet count and LDH response is achieved. Relapse is defined as having a platelet count greater than 50% decrease from the maximum platelet count and an LDH greater than 1.5 times the ULN. Relapse will be evaluated using the platelet count and the LDH collected within 1 week. Duration of response will be censored at the last platelet or LDH collection date if relapse does not occur during the study. Kaplan-Meier analysis of the duration of response will be performed for the patients who achieve a response by dose for the FAS population. Median duration of response will be presented with 95% CI.

Binary secondary efficacy endpoints will be summarized with exact 95% CI by dose for the FAS population. Non-responder imputation will be used to handle missing data.

CONFIDENTIAL

No use, disclosure or reproduction outside of Omeros without prior written authorization

In addition, efficacy laboratory values of platelet count, LDH, creatinine, hemoglobin, and haptoglobin will be plotted over time for the HSCT-TMA patients.

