Neutrophil engraftment date	Post-transplant, once	This is defined as the first date on which the neutrophil count is $\geq 0.5 \times 10^9/L$ for at least 3 consecutive measures on different days. This date is generally noted in the chart as the date of neutrophil engraftment. The chart-noted date will be used to define the engraftment date.
Platelet engraftment date	Post-transplant, once	Collect from clinical chart. This is defined as the first date on which the platelet count is $20 \times 10^9/L$ for at least 3 consecutive measures on different days with no platelet transfusions in previous 7 days. This date is generally noted in the chart as the date of platelet engraftment. The chart-noted date will be used to define the engraftment date.
Chimerism with dates	Post-transplant, each instance	The percent chimerism will be collected with the corresponding cell type (for each cell type measured – RBC, CD34+ cells, mononuclear cells, T-cells, B-cells, granulocytes, and natural killer cells as reported).
Graft failure	Post-transplant	The diagnosis of graft failure with the date will be noted as such and may be qualified as primary or secondary. If noted in the chart, the primary or secondary nature should be noted.
GVHD prophylaxis	At time of transplant and ongoing throughout the study	Prophylaxis for GVHD will generally be provided with immunosuppressive medications. Each medication, dose, and dates of administration will be collected. Changes in the medications or decreases in dose will provide support for the requirement that patients have persistent HSCT-TMA despite modification of immunosuppression. The modification may occur prior to the chart diagnosis of HSCT-TMA because physicians react to changes in some measures (e.g., increasing LDH) while another measure (e.g., platelet count) has not become abnormal, delaying the diagnosis of HSCT-TMA.
Patient Status (with dates)		
Vital status	Last patient follow-up, once	Collect as the latest of 1) the last clinic visit or telephone contact with the patient at which the patient was alive or 2) the date of death.
Cause of death	Last patient follow-up, once	Collect for patients who have died. If no cause of death is recorded, the cause will be reported as unknown.
Date of death	Last patient follow-up, once	Collect for the patients who die.
Patient Relapse Status (with dates)		

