Confusion/Cognitive impairment	Each instance at onset	Collect with the first date of diagnosis.
Seizures	Each instance at onset	Collect with the first date of diagnosis.
Hallucinations	Each instance at onset	Collect with the first date of diagnosis.
Other central nervous system	Each instance at onset	Other neurological signs and symptoms will be collected with the first date of diagnosis from the clinical chart.
Engraftment syndrome	At onset	Collect with dates.
Hypoxia	Each instance at onset	Collect with dates.
Pulmonary arterial Hypertension	At onset	Collect with dates.
Continuous positive airway pressure	Each instance at onset	Collect with dates.

CONFIDENTIAL

No use, disclosure or reproduction outside of Omeros without prior written authorization

Variables	Timing/Periodicity of Data Collection	Data Collection Rules/Definitions
Mechanical ventilation/ extracorporeal membrane oxygenation	Each instance at onset	Collect with dates from the clinical chart.
Tissue biopsy	Each instance at onset	Collect with dates and findings from the clinical chart.
Transfusions (date, number of units, ABO, and Rh type)		
Red blood cell	Each instance	Collect the number of units with date. ABO and Rh group of each unit will also be collected.
Whole blood	Each instance	Collect the number of units with date. ABO and Rh group of each unit will also be collected.
Platelets	Each instance	Collect the number of units with date. ABO will be collected for each instance.
Intravenous immunoglobulin	Each instance	Collect the number of units with date.
Plasma therapy	Each instance	Plasma therapy is defined as plasma exchange or plasma infusion. Collect each instance of plasma therapy with the date.
TMA Event		
Date of diagnosis	Each instance	HSCT-TMA is required for inclusion in the study. The date of diagnosis is the first day that a diagnosis of HSCT-TMA was recorded in the clinical chart.
Date of onset	Each instance	HSCT-TMA is required for inclusion in the study.
TMA treatment	Each instance	This will be determined by review of concomitant medications and episodes of plasma therapy.
Hospital Resource Utilization		
Hospitalization time	Following TMA diagnosis	Collect all dates of hospital admission and discharge.
Intensive care unit time	Following TMA diagnosis	Collect all dates of intensive care unit admission and discharge.

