2.8.2.2. Secondary Efficacy Endpoints

2.8.2.2.1. 100-day Survival

The 100-day survival status will be determined as a binary variable. A patient achieves a 100-day survival if the overall survival from the date of HSCT-TMA diagnosis of the patient is greater

than or equal to 100 days. If the 100-day survival status of a patient is unknown (i.e., censored before 100 days), this patient will be considered to have died prior to 100 days. The 100-day survival rate will be estimated with exact 95% CI by dose for the FAS population.

In addition, cumulative incidence at 100 days for each of the pre-specified cause of death (GVHD, graft failure, infections, progression of underlying disease, HSCT-TMA and other) will be estimated by a competing risks analysis (Section 2.8.2.2.2).

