2.8.2.2.2. Overall Survival

Overall survival will be calculated from the date of HSCT-TMA diagnosis. For the patients who are alive, their overall survival will be censored at the last known date of alive in the database. The method for handling a partially missing date of death is presented in Section 2.7.

Overall survival will be analyzed using Kaplan-Meier method by dose for the FAS population. Median overall survival and its 95% CI will be estimated by dose.

In addition, a competing risks analysis for overall survival will be performed. The cumulative incidence function of each pre-specified causes of death (GVHD, graft failure, infections, progression of underlying disease, HSCT-TMA, and others) will be estimated by nonparametric maximum likelihood method. The estimated cumulative incidence functions and their 95% CI will be displayed graphically.

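### SAP 2.7 sets a missing day to 1 for both diagnosis and death with no bound by other known dates, so survival times can be impossible and a partial diagnosis date can only lengthen survival

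*SAP*

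**What the plan says.** SAP 2.7 has three rules for incomplete dates.

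- TMA diagnosis: month and year are required. "If the day is missing, the day will be imputed as 1".
- Death, day missing: "if only the day of the death date is missing, the day will be imputed as the first day of the month".
- Death, month or year unknown: no imputation; the patient is censored when last known alive.

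The last-known-alive date is therefore used to censor, both here and for patients who are alive. It is not used as a floor for an imputed death.

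Both survival endpoints start at diagnosis. SAP 2.8.2.2.2 states: "Overall survival will be calculated from the date of HSCT-TMA diagnosis". For partial death dates it refers back to 2.7 and adds no check. Under Protocol 13.2.5.2 a patient is a 100-day survivor "if the overall survival from the date of HSCT-TMA diagnosis of the patient is ≥ 100 days". SAP 2.8.2.2.1 reports that rate by dose. No sensitivity analysis for imputed dates is listed.

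**The concern.** The two rules look alike but act in opposite directions. Day 1 is the earliest possible day. For a death it is conservative for survival, but without a floor it can fall before a visit, a dose or the diagnosis itself. For a diagnosis it lengthens survival or leaves it unchanged, and it can fall before the transplant.

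The SAP's safeguard for unknown status does not correct this: "If the 100-day survival status of a patient is unknown (i.e., censored before 100 days), this patient will be considered to have died". It applies to censored patients. A patient with a recorded death and an imputed diagnosis day is not censored.

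At stake are overall survival, 100-day survival, the competing-risks analysis of cause of death, and the descriptive times to and from diagnosis in SAP 3.2.4. The protocol's introduction says survival has already been compared with a literature-based historical control, so the accuracy of the survival origin matters.

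**Working it through.** **Inputs.** The imputation rules are in SAP 2.7, and the 100-day threshold is in Protocol 13.2.5.2. The expected number of HSCT-TMA patients is about 28 (SAP 1.3). SAP Table 1 gives 2 + 22 = 24 at 4.0 mg/kg and 4 at 370 mg. The number of partial dates is not given, so effects are shown per affected patient. Days are assumed uniform over a 31-day month, and survival is the difference between dates.

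**The plan's own figure.** The SAP gives no figure for date imputation. Its precision statement for n = 28 does reproduce. Clopper-Pearson limits for 14/28 are 30.6% and 69.4%, and widths over all possible counts run from 12.3% to 38.7%. This confirms only the denominator used below.

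**Size of the shift.** A true day D set to 1 moves the date D − 1 days earlier. The range is 0 to 30 days in a 31-day month (maximum 29 in a 30-day month, 27 in a 28-day February). The mean over 31 days is 30/2 = 15.

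**Partial diagnosis date, true survival t below 100.** Imputed survival is t + (D − 1). It reaches 100 when D ≥ 101 − t, which is t − 69 of the 31 days, for t from 70 to 99.

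| True survival (days) | Chance of being counted as a 100-day survivor |
|---|---|
| 70 | 1/31 = 3% |
| 85 | 16/31 = 52% |
| 99 | 30/31 = 97% |

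Example (non-leap year): diagnosis 31 January, death 15 April.

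- True survival: 28 + 31 + 15 = 74 days.
- Under the rule, diagnosis becomes 1 January: 74 + 30 = 104 days, a 100-day survivor.
- Mid-month diagnosis (15 January): 90 days.
- Latest day in the month: 74 days.

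**Partial death date, true survival t of 100 or more.** Imputed survival is t − (D − 1). It falls below 100 on 130 − t of the 31 days, for t from 100 to 129. That is 30/31 = 97% at 100 days, 15/31 = 48% at 115 and 1/31 = 3% at 129. These errors count against the drug.

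**Both dates partial.** The net shift runs from −30 to +30 days, with mean 0.

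**Impossible values.** Take diagnosis on 10 March, first dose on 15 March, last known alive on 20 March, and true death on 25 March with the day missing.

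- True survival: 15 days.
- Under the rule, death is 1 March: 19 days before last known alive, 14 days before first dose, and survival is 1 − 10 = −9 days.
- With a floor at the last-known-alive date: 20 − 10 = 10 days.

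The SAP does not say how a negative time enters the Kaplan-Meier or competing-risks analyses. If it were dropped, an early death would leave the analysis, which is not conservative.

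For diagnosis, take transplant on 10 March and diagnosis on 28 March with the day missing. The time from transplant to diagnosis is 18 days, but the rule gives 1 − 10 = −9 days.

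**Effect per reclassified patient.** 1/28 = 3.6 points overall and 1/4 = 25 points in the 370 mg group.

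**The case against.** A reader might infer that partial dates are common because the supplemental data come from medical records. The documents give no count, and several provisions point the other way:

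- The diagnosis date is recorded at screening (Protocol 10.1.2.1).
- Protocol 19.4 ties it to a chart entry: "The date of diagnosis is the first day that a diagnosis of HSCT-TMA was recorded in the clinical chart".
- Protocol 19.5 collects local laboratory values daily from 28 days before diagnosis, which needs the exact day.
- Deaths are reported within 24 hours of site awareness, and adverse events are collected to the last follow-up visit, Day 92 in this cohort. Day 92 is 91 days after first dose. If diagnosis was at least 9 days before first dose, the 100-day window lies within that reporting period (9 + 91 = 100).

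A reader might also infer that the pair of rules inflates survival, or that nothing checks these dates. Neither follows. The death rule alone shortens survival. Protocol 15 sends missing data and anomalies to the sites for resolution, and the SAP 2.7 listings already show partial dates.

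A further tempting reading is that the primary response endpoint is biased. Protocol 13.2.1 takes baseline creatinine as the maximum from TMA diagnosis to 4 weeks after first dose. An earlier diagnosis date could raise that maximum and make the creatinine criteria easier to meet. SAP 2.5 instead uses the last value before first dose, which does not depend on the diagnosis date. The link exists only if the protocol's window is applied.

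These arguments make the problem less likely and smaller. They do not remove it. Site queries come before imputation and do not constrain the imputed value, and a listing shows a partial date without correcting the survival time derived from it.

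**Conclusion.** The point holds as a minor defect in a stated rule. Followed as written, SAP 2.7 can place a death before a recorded alive date, and it always gives a partial diagnosis date the value most favourable to survival. The shift is 0 to 30 days in each case, with a mean of about 15 if days are uniform. Each reclassified patient moves the 100-day rate by 3.6 points overall, or 25 points in the four-patient 370 mg group.

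The per-patient figures rest on the uniform-day assumption and on 28 patients. The total effect cannot be stated and may be nil. It falls mainly on secondary, descriptive survival endpoints. The documents do not support a claim that survival is in fact overstated.

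**What to change.** Amend SAP 2.7 as follows.

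1. **Death, day missing.** Use the later of the first of the recorded month and the last-known-alive date itself, kept within the recorded month. Adding a day to the last contact would not work: last alive on 31 May with death recorded in May would give 1 June. If the last-known-alive date falls after the recorded month, query the site.
2. **Diagnosis, day missing.** Require the imputed date to be not before transplant and not after first dose. Because day 1 favours longer survival, use the latest consistent day in the recorded month. This shifts any error towards shorter survival, so if the sponsor prefers another primary rule, run it at least as a sensitivity analysis for overall and 100-day survival.

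The bounding dates are already collected. Protocol 19.4 records the transplant date and, under vital status, "the last clinic visit or telephone contact with the patient at which the patient was alive" or the date of death, whichever is later. For a patient who died, the last alive contact may therefore have to be derived from dated visits, doses or laboratory samples.

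The cost is a few sentences and one sensitivity analysis, with no new data. The downside is that survival may be slightly shorter for patients with a partial diagnosis date.
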